## 4.0 Study Design

4.1 *Describe and explain the study design (e.g. case-control, cross-sectional, ethnographic, experimental, interventional, longitudinal, observational).*

Response: A single-center, single-blind, randomized controlled clinical trial:

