**Primary Endpoints:**

1. **Change in Probing pocket depth (PPD) at the 6-month post-SRP completed at Baseline.**

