**Group A: Diabetic, Scaling & Root Planing (SRP) + Paroex® + Soft-Picks**

**Group B: Non-Diabetic, SRP + Paroex® + Soft-Picks**

**Group C: Diabetic, SRP**

**Group D: Non-Diabetic, SRP**

## 5.0 Local Number of Subjects

5.1 *Indicate the total number of subjects that will be enrolled or records that will be reviewed locally.*

Response: **104 with complete data; 26 per group**

5.2 *If applicable, indicate how many subjects you expect to screen to reach your target sample (i.e. your screen failure rate).*

Response: **250**

5.3 *Justify the feasibility of recruiting the proposed number of eligible subjects within the anticipated recruitment period. For example, how many potential subjects do you have access to? What percentage of those potential subjects do you need to recruit?*

Response: **We have a list of participants in previous studies that have given us permission to re-contact them about new studies. We also have a successful history of being able to make and surpass recruitment goals. Tactics such as word of mouth, flyers and posters, and ads have worked well in the past.**

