### 9.2 *Describe how you will protect the privacy interests of prospective subjects during the recruitment process.*

*NOTE: Privacy refers to an individual's right to control access to him or herself.*

**Response:** Potential and enrolled participants will interact with the study staff, the dentists, registered dental hygienists, dental assistants, laboratory technicians, research associates and data manager, in an operatory in the PDRC. If participants chose NOT to interact with one of these people, we can accommodate the request to a limited degree by having another dentist, hygienist, dental assistant or laboratory technician “work” with them, but once seen/examined by a dentist or hygienist we need to keep the same examiner for consistency of clinical examination data. Participants can ask to be seen in an operatory with a door that can be closed to better ensure privacy. Participants may also choose not to answer questions, but if those questions provide critical information needed to answer the research questions, the person will not be allowed to remain in the study. When participants have samples such as saliva collected, they are provided privacy from the view of others; blood is collected and height and weight measured out of the view of others as well.

The PDRC is a suite of rooms and operatories some of which have doors for privacy and quiet. However, even operatories without doors have limited access and view and so provide a good degree of privacy to everyone.

Participants “self-select” to join the study by calling us in response to flyers, posters and ads. They are told they may withdraw from the study at any time with no adverse effects on them. They are told we need certain data and that data need is explained prior to enrollment (at the time of the screening call and during the screening visit/first study visit.

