#### 3-MONTH VISIT:

1. Collect the unused Soft-Picks and Paroex® bottle from the participants in the Groups A and B.

2. Ask the subjects to answer the Adverse Event, Taste and Compliance questionnaire.

3. Review medical and dental histories.

4. Taste Test.

5. Oral health examination

6. Collect saliva, subgingival plaque and stool/fecal samples.

6. Anterior teeth cleaning: All subjects will receive anterior teeth cleaning.

7. Groups A and B will have the product, Soft-Picks, replenished and usage instructions reviewed as needed.

8. Make or confirm the next appointment.

9. If any sites where pocket depths stay the same and are  $\geq 5$  mm or if the pockets deepen, periodontal treatment will be repeated.

Exact treatment will be determined by the clinician (dentist or periodontist). The treatment will be explained to the participant and questions will be answered beforehand. Options for Rescue Therapy treatment are:

- Option 1: No additional treatment.
- Option 2: Pocket depths of  $\geq 5$  mm will receive scaling and root planing,
- Option 3: Pocket depths of  $\geq 5$  mm will receive scaling and root planing with the addition of a local antimicrobial agent,

- **Option 4:** Pocket depths of  $\geq 5$  mm will receive modified Widman flap surgery,
- **Option 5:** Pocket depths of  $\geq 5$  mm will receive modified Widman flap surgery with the addition of the GUIDOR® *easy-graft®* CLASSIC Alloplastic Bone Grafting System to infrabony defects that are amenable to regeneration.

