#### **6-MONTH VISIT:**

1. Collect the unused Soft-Picks from the subjects in the Test Group.
2. Ask the subjects to answer the Adverse Event, Taste and Compliance questionnaire.
3. Review medical and dental histories.
4. Taste Test.
5. Oral health examination
6. Collect samples: blood (FBS, HbA1c, Insulin, hs-CRP and microbiome testing, and for future testing of C-peptide, proinsulin, total GLP-1, PYY, DPP-IV, glucagon, LPS, soluble-TNF $\alpha$  RI and RII, MGO, TMAO, creatinine, and for future unknown testing), subgingival plaque, saliva, fecal, skin, and vaginal samples.
7. Retreat all PD  $\geq 5$  mm sites. Subjects will receive additional treatment (Rescue Therapy), including surgery and/or topical or systemic antibiotics, if a clinician (dentist or periodontist) decides they need it. Rescue Therapy is standard of care for non-responsive periodontal lesions, the type depending on the clinical status of the participant. The need for Rescue Therapy (yes, no and type) will be noted in the study records and considered in the analysis of the study data. If on examination, a participant presents with an area showing a clinically defined worsening of their periodontal condition, rescue therapy will be initiated. This therapy will reduce the chance of the tooth being lost from periodontal disease. Rescue therapy will be provided to sites that remain at  $\geq 5$  mm or those demonstrating an increase in pocket depths of  $\geq 2$  mm from the baseline visit bringing them to or above the 5 mm level. Treatment will consist of scaling and root planing of the affected tooth and if the pocket depth is  $\geq 5$  mm, the site may also be treated by local drug delivery with Arestin. In women of childbearing potential, a urine pregnancy test will be provided prior to the placement of Arestin. If the pregnancy test is positive, Arestin will not be used in treatment. Local anesthetic may be used during the procedure as needed. Other treatments for saving the tooth may be given as deemed necessary by the dentist/periodontist clinician, as described above (Number 9 of the 3-

**month Visit).** The clinician will discuss the additional treatment with the participant before it is provided. The clinician providing the rescue therapy in a given subject should not be the clinician that will provide the periodontal measurements for that participant during the study.

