**Dental radiographs:** About 18 radiographs will be taken. These x-rays will not be taken if suitable x-rays taken in the past two years are available to review, or if the dental clinician feels there is no clinical need for them. The amount of radiation exposure from the dental x-rays in this study is about 17.1 millirem (or 0.017 rem). This amount is below the 5 rem per year allowed for research participants by the National Institutes of Health (NIH) Radiation Safety Committee. The average person in the United States has a radiation exposure of about 0.36 rem per year from natural sources, such as the sun, outer space, and earth's air and soil. When taking x-rays, the lowest dose possible will be used and participants will wear a lead apron to reduce exposure.

Although there is no direct evidence that the amount of radiation exposure from participating in this study is harmful, there is indirect evidence that it may not be completely safe. There may be a very slightly increased risk of cancer.

Paroex® is a non-alcohol chlorhexidine preparation. With use of chlorhexidine, there is risk of reversible staining of teeth and the possibility of some alteration in taste. There is increased likelihood of staining in smokers, coffee drinkers and those who are susceptible to teeth staining in general. The cleaning of the front teeth that will be

**provided at the 3-month visit will help to reduce any staining that may occur. If there is any alteration in taste, it should go away when use of chlorhexidine stops. Paroex® was approved by the FDA November 29, 2005 (application # (ANDA) 076434).**

**Soft-Picks may cause some bleeding of the gums at first usage, but the bleeding should lessen and stop as use is continued (as gums heal). Soft-Picks are a readily available consumer product sold in supermarkets and drug stores. They are “510(k) exempt” from requiring FDA approval.**

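### The masked party is not named, and product return from the rinse-and-picks arms is listed before the probing at every follow-up visit with no stated rule keeping the examiner away from it

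*Combined protocol and SAP*

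**What the plan says.** **Masking.** The only statement on blinding is the label in Section 4.1, "A single-center, single-blind, randomized controlled clinical trial". It does not say who is masked.

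**Arms.** Two arms receive scaling and root planing (SRP) plus the rinse and picks, for example "Group A: Diabetic, Scaling & Root Planing (SRP) + Paroex® + Soft-Picks". The other two, C and D, receive SRP alone, with no placebo rinse or sham pick listed.

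**Primary endpoint.** "Change in Probing pocket depth (PPD) at the 6-month post-SRP completed at Baseline", which a clinician measures by probing.

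**Follow-up visits (Section 10.1).** At 3 months item 1 is "Collect the unused Soft-Picks and Paroex® bottle from the participants in the Groups A and B". At 6 months it is "Collect the unused Soft-Picks from the subjects in the Test Group", a term not defined elsewhere but presumably meaning Groups A and B. At 9 and 12 months item 1 is again the return of picks from Groups A and B. A questionnaire follows at each visit, at 6 months worded "Ask the subjects to answer the Adverse Event, Taste and Compliance questionnaire". The oral examination comes later in every list.

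**Examiner.** Section 9.2 says that "once seen/examined by a dentist or hygienist we need to keep the same examiner for consistency of clinical examination data". The 6-month visit text adds that the clinician who gives rescue therapy should not be the one who measures that participant. No other separation of roles is visible.

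**Staining.** Section 21.1 says of chlorhexidine that "there is risk of reversible staining of teeth and the possibility of some alteration in taste".

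**The concern.** Without a placebo, participants cannot be masked. The single-blind label therefore has content only if the person holding the probe does not know the arm. Collecting product from some participants and not others marks the arm directly, and the plan lists that step before the probing at all four follow-up visits, including the primary one. If the examiner performs or sees it, the reading is taken with the arm known.

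Because one examiner is kept for each participant, a single disclosure would carry through to every later visit. The readings also have a second use. Pocket depths at or above 5 mm feed the decision on rescue therapy, and needing rescue therapy is how Section 1.2 defines a Poor Responder. A reading influenced by knowledge of the arm could thus affect both the primary endpoint and the responder classification.

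**Working it through.** **Step 1. Order of items at each follow-up visit (Section 10.1).**

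| Visit | Product return | Questionnaire | Oral examination | Replenishment |
|---|---|---|---|---|
| 3 months | item 1, Groups A and B | item 2, all subjects | item 5 | item 7 |
| 6 months (primary) | item 1, Test Group | item 2, all subjects | item 5 | item 8 |
| 9 months | item 1, Groups A and B | item 2, all subjects | item 5 | item 7 |
| 12 months | item 1, Groups A and B | item 3, all subjects | item 6 | none listed |

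Only product return is both specific to an arm and listed before the examination. The questionnaire goes to everyone, so giving it does not mark the arm, although the answers on taste and compliance may. Replenishment already follows the examination wherever it is listed. At baseline, randomization and product hand-out are listed after the examination, so the baseline reading is not in question.

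**Step 2. Which rules shield the examiner?** The rescue-therapy rule covers one task only. Nothing visible covers product return, replenishment, product instruction, the questionnaire, or access to allocation and product records. Overlap of roles is possible: Section 21.1 lets a dentist or a hygienist examine, and at baseline a hygienist gives oral hygiene instruction at the visit where Groups A and B receive product.

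**Step 3. The plan's own sample-size figure.** Section 17.2 gives 24 per group, SD 0.5, about 80% power and alpha 0.05, for a difference of 35%. The 35% has no base and no value in millimetres, and the SD has no unit, so 24 cannot be reproduced without an assumption. This point does not depend on it. Only n = 24 and SD = 0.5 are carried forward, with the SD taken as mm.

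**Step 4. Illustration of what a differential shift would do.** Take a two-sided t-test at 0.05 with no true effect, and let knowledge of the arm shift the mean difference by b.

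- SE = 0.5 × √(2/24) = 0.144 mm, with df = 2 × 24 − 2 = 46.
- Non-centrality = b / SE. The rejection probability comes from the non-central t distribution.

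| Assumed b (mm) | b / SE | Type I error |
|---|---|---|
| 0 | 0 | 5.0% |
| 0.05 | 0.35 | 6.3% |
| 0.10 | 0.69 | 10.4% |
| 0.20 | 1.39 | 27.4% |

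A normal approximation gives 6.4%, 10.7% and 28.3%. If the arms are pooled as 48 against 48 (A+B against C+D), SE = 0.5 × √(2/48) = 0.102 mm and the t-test values are 7.7%, 16.3% and 49.2%. A fixed bias does more harm in the larger comparison because the standard error is smaller.

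The documents give no figure for b. These rows show how sensitive the test is to a small shift. They do not estimate bias in this trial.

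**The case against.** The strongest reply is that nothing shows the examiner learning the arm. The lists follow the participant through the visit and do not say who does each item. Section 9.2 names assistants, laboratory technicians and research associates as well as dentists and hygienists, and Section 12.1 describes six operatories, so another person could collect product out of the examiner's sight. The numbering is also an imperfect guide to sequence: the baseline list returns to 3 after item 4, the 3-month list has two items numbered 6, and at 3 months the next appointment is listed before any repeat treatment. Part of Section 14 is not in the public text, and the Manual of Procedures that Section 10.3 cites was not available, so roles may be assigned there.

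All of this stands against the stronger reading that a reader might infer, namely that the visit order reveals the arm before probing and so defeats the blinding. The documents do not support that. Nor do they support treating the questionnaire as equivalent to product return.

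Two further replies carry less weight. Section 14.4 calibrates examiners to a gold standard, but calibration limits inconsistency between examiners and does not remove a shift that depends on the arm. Section 21.1 says that the 3-month cleaning of the front teeth will help to reduce staining. That may narrow this second route, but it has no bearing on product return.

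What remains is that Section 10.1 is the plan's account of how visits run. It lists an arm-specific step before the primary measurement and states no safeguard.

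**Conclusion.** The concern holds in a limited form. The masked party is undefined, and the listed order at all four follow-up visits leaves an avoidable route by which the examiner could learn the arm before probing. Whether that happens cannot be determined from the documents.

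The size is unknown. Under assumed shifts of 0.05 to 0.20 mm, with SD 0.5 read as mm and 24 per group, type I error would run from about 6% to 27%. A reader might want to set those shifts against an expected treatment difference in millimetres, but Section 17.2 gives only a percentage without a base, so that comparison cannot be made.

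The change is worth making because it costs little and protects a hand-probed primary endpoint. The sample size and power statement are unaffected.

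**What to change.** - **Section 4.1:** name the periodontal examiner as the masked party and state that participants are not masked.
- **Section 10.1, at 3, 6, 9 and 12 months:** move product return after the oral examination. The medical and dental history review can stay where it is, and replenishment needs no move.
- **Roles:** have existing staff other than that participant's examiner handle product return, replenishment, product instruction and the taste and compliance questionnaire. Keep allocation and product records from the examiner.
- **Participants:** ask them not to tell the examiner which products they use.
- **Optional check:** record the examiner's guess of the arm at 6 months, so that the success of masking can be reported.
- **Visits already completed:** report who performed these steps.

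**Cost:** revised visit checklists and minor changes to visit flow, with no added visit or measurement. Since the study is now unfunded and some staffing text is not public, the site should confirm that a second person is available at each visit. Staining and participants' remarks can still unmask some participants, so masking would be improved but not complete.

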**Group A: Diabetic, Scaling & Root Planing (SRP) + Paroex® + Soft-Picks**

**Group B: Non-Diabetic, SRP + Paroex® + Soft-Picks**

**Group C: Diabetic, SRP**

**Group D: Non-Diabetic, SRP**

## 5.0 Local Number of Subjects

5.1 *Indicate the total number of subjects that will be enrolled or records that will be reviewed locally.*

Response: **104 with complete data; 26 per group**

5.2 *If applicable, indicate how many subjects you expect to screen to reach your target sample (i.e. your screen failure rate).*

Response: **250**

5.3 *Justify the feasibility of recruiting the proposed number of eligible subjects within the anticipated recruitment period. For example, how many potential subjects do you have access to? What percentage of those potential subjects do you need to recruit?*

Response: **We have a list of participants in previous studies that have given us permission to re-contact them about new studies. We also have a successful history of being able to make and surpass recruitment goals. Tactics such as word of mouth, flyers and posters, and ads have worked well in the past.**

## 6.0 Inclusion and Exclusion Criteria

6.1 *Describe the criteria that define who will be **included** in your final study sample.*

*NOTE: This may be done in bullet point fashion.*

**Response: Inclusion Criteria:** To be in this study subjects must meet all of the following criteria:

- 1) Be able to understand the informed consent form and be willing and able to read and sign it.
- 2) At least 25 years of age.
- 3) Be able to understand and follow directions for study procedures.
- 4) At least 14 natural teeth, not counting third molars (“wisdom teeth”).
- 5) For moderate periodontal disease: At least four (4) teeth with at least one (1) site with  $\geq 5$  mm pocket depth (PD) and at least two (2) of the affected teeth with  $\geq 2$  mm alveolar bone loss as shown on radiographs. For Severe periodontal disease: At least eight (8) teeth with at least one (1) site with  $\geq 5$  mm pocket depth (PD) and at least two (2) of the affected teeth with  $\geq 2$  mm alveolar bone loss as shown on radiographs.

6.2 *Describe the criteria that define who will be **excluded** from your final study sample.*

*NOTE: This may be done in bullet point fashion.*

**Response: Exclusion Criteria:** Presence of the following criteria results in ineligibility for this study;

- 1) Presence of orthodontic appliances (“braces”).
- 2) An abnormal condition of lips, lining of the mouth, tongue, or gums (except for periodontal disease). If subject has a cold sore, canker sore, or injury in their mouth, they may return after the sore or injury heals.
- 3) Abscess of the gingiva caused by periodontal disease, or visible gross tooth decay
- 4) A broken tooth root or an abscessed tooth, per clinician’s judgement. Subject may be allowed to participate in the study after the condition is successfully treated or the study dentist reviews the condition and does not feel it will jeopardize the results of the study.
- 5) Periodontal treatment in the past 6 months.
6. Antibiotic therapy in the past three (3) months.

- 7) Have used cigarettes or other tobacco products in the past year.
- 8) Body mass index (BMI) is  $> 45$ .
- 9) Have regularly used non-steroidal anti-inflammatory drugs (such as  $\geq 325$  mg aspirin or ibuprofen) over the past 3 weeks.
- 10) Regularly using drugs that weaken the immune system (such as corticosteroids taken by mouth or injection, and cyclosporine).
- 11) Have participated in another clinical research study in the past 30 days.
- 12) Pregnant or breastfeeding.
- 13) Have a condition that we feel will make study participation unsafe or difficult for the patient.
- 14) Require premedication for dental exams.

6.3 *Indicate specifically whether you will include any of the following special populations in your study using the checkboxes below.*

***NOTE: Members of special populations may not be targeted for enrollment in your study unless you indicate this in your inclusion criteria.***

Response: **None.**

- Adults unable to consent
- Individuals who are not yet adults (infants, children, teenagers)
- Pregnant women
- Prisoners

6.4 *Indicate whether you will include non-English speaking individuals in your study. Provide justification if you will exclude non-English speaking individuals.*

*In order to meet one of the primary ethical principles of equitable selection of subjects, non-English speaking individuals may **not** be routinely excluded from research as a matter of convenience.*

*In cases where the research is of therapeutic intent or is designed to investigate areas that would necessarily require certain populations who may not speak English, the researcher is required to make efforts to recruit and include non-English speaking individuals. However, there are studies in which it would be reasonable to limit subjects to those who speak English. Some examples include pilot studies, small unfunded studies with validated instruments not available in other languages, studies with numerous questionnaires, and some non-therapeutic studies which offer no direct benefit.*

Response: We will not be actively recruiting non-English speaking subjects. This is a pilot study with the aim to obtain preliminary data that can be used for a larger proposal in the future. The expected number of subjects needed for this pilot does not warrant having the consent and surveys all officially translated into another language.

## 7.0 Vulnerable Populations

*If the research involves special populations that are considered vulnerable, describe the safeguards included to protect their rights and welfare.*

*NOTE: You should refer to the appropriate checklists, referenced below, to ensure you have provided adequate detail regarding safeguards and protections. You do not, however, need to provide these checklists to the IRB.*

7.1 *For research that involves **pregnant women**, safeguards include:*

*NOTE CHECKLIST: Pregnant Women (HRP-412)*

Response:

**N/A:** This research does not involve pregnant women.

7.2 *For research that involves **neonates of uncertain viability or non-viable neonates**, safeguards include:*

*NOTE CHECKLISTS: Non-Viable Neonates (HRP-413), or Neonates of Uncertain Viability (HRP-414)*

Response:

**N/A:** This research does not involve non-viable neonates or neonates of uncertain viability.

7.3 *For research that involves **prisoners**, safeguards include:*

*NOTE CHECKLIST: Prisoners (HRP-415)*

Response:

**N/A:** This research does not involve prisoners.

7.4 *For research that involves **persons who have not attained the legal age for consent to treatments or procedures involved in the research (“children”)**, safeguards include:*

*NOTE CHECKLIST: Children (HRP-416)*

Response:

**N/A:** This research does not involve persons who have not attained the legal age for consent to treatments or procedures (“children”).

7.5 *For research that involves **cognitively impaired adults**, safeguards include:*

Response:

**N/A:** This research does not involve cognitively impaired adults.

7.6 *Consider if other specifically targeted populations such as students, employees of a specific firm, or educationally or economically disadvantaged persons are vulnerable. Provide information regarding their safeguards and protections, including safeguards to eliminate coercion or undue influence.*

Response: Students and employees may be screened and enrolled in the study if they meet eligibility criteria. However, their enrollment is not tied to student status or grades nor employee performance or evaluations.

